7.2 Serious Adverse Events (SAEs)

All AEs meeting the definition of SAE will be collected. An SAE is defined as any AE which results in at least one of the following outcomes:

- Initial inpatient hospitalization or prolongation of existing inpatient hospitalization
- A life-threatening event, i.e., an event in which the subject was at immediate risk of dying at the time of the event; not an event that hypothetically could have caused death had it been more severe
- Persistent or significant disability or incapacity
- Congenital anomaly or birth defect in offspring
- Death
- Is deemed serious for any other reason, i.e., if it is an important medical event based on appropriate medical judgement which may jeopardize the subject and may require medical or surgical intervention to prevent one of the other listed outcomes.

7.2.1 Reporting Period of Serious Adverse Events (SAEs)

SAEs will be reported from randomization until EOS at month 12, or until the subject withdraws from the study. Study clinicians will follow SAEs that occur in any subject during this study in a manner consistent with routine clinical practice.

The study clinician is responsible for alerting Novo Nordisk or its designee to any SAE within 24 hours of becoming aware of it via electronic data capture (EDC) entry. The subject should be followed until the outcome of the event is closed out. Follow-up information should be reported within 24 hours of it becoming available. Requests for follow-up information should be resolved within 14 calendar days.

The study clinician is responsible for assessment of causality and outcome of SAEs, as defined in Appendix 3. Causality and outcome should be provided at the time of reporting an SAE.

If an investigator becomes aware of SAEs after EOS at end of month 12, that are possibly related to the study product, these should be reported as spontaneous events.

7.3 Pregnancy

Any abnormal pregnancy outcome (e.g., spontaneous miscarriage, fetal death, congenital anomaly/birth defect, etc.) is considered an SAE. For the purposes of this study, any pregnancies in participating female subjects will be reported, along with pregnancy outcome and any AEs or SAEs observed in the fetus or newborn until 1 month of age.

7.3.1 Reporting Period of Pregnancy

Pregnancies will be reported from the time a subject is randomized until EOS at month 12 or until the subject withdraws from the study. Information will be recorded on the appropriate form and submitted to Novo Nordisk within 14 calendar days of learning of a subject's pregnancy. The subject will be followed to determine the outcome of the pregnancy. The study physician will collect follow-up information on subject and neonate, which will be forwarded to Novo Nordisk. Any termination of pregnancy should be reported, regardless of fetal status (presence or absence of anomalies) or indication for procedure. A spontaneous abortion is always considered to be an SAE and should be reported as such.

7.4 Technical Complaints

Technical complaints may be reported as per usual practice and local regulations. However, any SAEs resulting from a technical complaint must be reported via the EDC.

8 DATA COLLECTION

8.1 Data Sources

Data sources include primary data collected prospectively by study site at study visits (demographic and clinical data, subject-completed PRO data) and entered into the eCRF, as well as secondary data collection utilizing pharmacy dispensing data. In order to maintain subject confidentiality, each subject will be assigned a unique subject study ID number upon signing informed consent to use in place of subject name or any other identifying information (e.g., medical record number). Primary eCRF data and pharmacy derived variables will be integrated into one analysis dataset.

8.2 Electronic Case Report Forms (eCRFs)

Study data prospectively collected at the study site will be entered into eCRF by trained site study personnel through a fully validated, 21 CFR 11 and HIPAA compliant EDC system. Subjects will complete PRO questionnaires on paper and the site study personnel will enter the completed forms into the EDC system. Site users will be provided eCRF Completion Guidelines (eCCGs) to assist with study data collection and entry. Study personnel will access the EDC system through a secure study website.

The study clinician has the ultimate responsibility for the collection and reporting of all study data through the eCRFs, as well as ensuring that they are accurate and complete to the extent possible.

8.3 Database Lock

Database lock will occur once data collection of the last subject follow up visit and data management activities are complete.

9 STUDY MANAGEMENT

9.1 Regulatory and Ethical Consideration

All study activities will be conducted in accordance with Good Clinical Practice (GCP) guidelines. Study personnel at clinician sites will be provided training on the study protocol, the Informed Consent Form (ICF), data collection, and data entry to ensure both the protection of potential study subjects as well as the scientific integrity of the study. Site monitoring will be conducted by HealthCore staff.

9.1.1 Institutional Review Board (IRB)

The study clinician will have prospective IRB approval of the study protocol, ICF, and any subject information or recruiting materials prior to commencement of any study activities at his/her site. In the case of a protocol amendment, the study clinician must sign the revised protocol and submit the amendment to the IRB for review and approval prior to implementation of any changes specified in the protocol amendment. All changes in research activity and all unanticipated problems involving risk to human subjects or others must be reported to the IRB as required.

The study clinician will obtain continued review of the IRB study approval at intervals not to exceed one year or otherwise specified by the IRB.

9.1.2 Informed Consent

An ICF describing the purpose, procedures, and potential risks and benefits of the study will be developed and approved by the IRB prior to study initiation. Written informed consent will be obtained prior to initiation of any study-related procedures. Each subject will receive a copy of

the signed ICF. The study clinician will retain the original signed ICF for each subject. The IRB must prospectively approve any changes to the ICF during the course of the study before use.

If a protocol amendment increases the potential risk to the subject, the ICF must be revised and submitted to the IRB for review and approval prior to implementation. The revised ICF must then be used to obtain consent from new subjects entering the study as well as from currently enrolled subjects if they are affected by the amendment, per IRB guidance.

9.2 Record Retention and Access

This study may be subject to audits or inspections by regulatory authorities or Novo Nordisk (or its designee). To enable such inspections and/or audits, the study clinician must agree to maintain and allow access to required subject and study records. The study clinician agrees to keep the identity of all participating subjects (sufficient information to link records, e.g., hospital records), all original signed ICFs, source documents, detailed records of treatment disposition, and adequate documentation of relevant correspondence (e.g., letters, meeting minutes, telephone calls, reports) as specified in the Clinical Study Agreement.

10 PUBLICATION OF STUDY RESULTS

All information collected for this study is considered confidential information belonging to Novo Nordisk. Information regarding the study will be disclosed at clinicaltrials.gov and novonordisk-trials.com. It will also be disclosed according to other applicable requirements such as those of the International Committee of Medical Journal Editors (ICMJE) [23], the Food and Drug Administration Amendment Act (FDAAA) [24], European Commission Requirements [25] [26] and other relevant recommendations or regulations. If a subject requests to be included in the trial via the Novo Nordisk e-mail contact at these web sites, Novo Nordisk may disclose the investigator's contact details to the subject. As a result of increasing requirements for transparency, some countries require public disclosure of investigator names and their affiliations.

The Primary Completion Date (PCD) is the last assessment of the primary endpoint, and is for this trial Last Subject First Visit (LSFV) + 12 months (-14 days +28) corresponding to visit 13. If the last subject is withdrawn early, the PCD is considered the date when the last subject would have completed visit 13. The PCD determines the deadline for results disclosure at clinicaltrials.gov according to FDAAA.

A final study report will be generated following completion of data collection and analysis. Results and findings will be submitted to conferences and for publication in peer-reviewed scientific journals. Novo Nordisk reserves the right to postpone publication and/or communication for up to 60 days to protect intellectual property.

Novo Nordisk commits to communicating, and otherwise making available for public disclosure, results of studies regardless of outcome. Public disclosure includes publication of a paper in a

scientific journal, abstract submission with a poster or oral presentation at a scientific meeting, or disclosure by other means.

The results of this study will be subject to public disclosure on external web sites according to international and national regulations, as reflected in the Novo Nordisk Code of Conduct for Clinical Trial Disclosure.

11 INDEMNIFICATION

Novo Nordisk carries product liability for its products, and liability as assumed under the special laws, acts and/or guidelines for conducting clinical trials in any country, unless others have shown negligence.

Novo Nordisk assumes no liability in the event of negligence or any other liability of the sites or investigators conducting the trial or by persons for whom the said site or investigator are responsible.

Appendix 1-1: Time and Events Schedule

Study NN8022-4432	Screening and Randomization	Weight Management Program											
		V2	V3	V4	V5	V6	V7	V8	V9	V10	V11	V12	V13
Visit (V)	V1	V2	V3	V4	V5	V6	V7	V8	V9	V10	V11	V12	V13
Timing of visit (months)	0	1	2	3	4	5	6	7	8	9	10	11	12
Visit window (days)	0	±14	±14	±14	±14	±14	±14	±14	±14	±14	±14	±14	-14, +28
SUBJECT-RELATED INFORMATION AND ASSESSMENTS													
Informed consent	X												
Demography ^a	X												
Inclusion criteria	X												
Exclusion criteria	X												
Randomization	X												
Medical history/concomitant illness	X												
Concomitant medication	X												
Disallowed medication ^b		X	X	X	X	X	X	X	X	X	X	X	X

Study NN8022-4432	Screening and Randomization	Weight Management Program											
		V2	V3	V4	V5	V6	V7	V8	V9	V10	V11	V12	V13
Visit (V)	V1												
Timing of visit (months)	0	1	2	3	4	5	6	7	8	9	10	11	12
Visit window (days)	0	±14	±14	±14	±14	±14	±14	±14	±14	±14	±14	±14	-14, +28
EFFICACY													
Height	X												
Body weight	X	X	X	X	X	X	X	X	X	X	X	X	X ^c
WPAI-SHP	X						X						X
WLQ-8	X						X						X
SMA attendance		X	X	X	X	X	X	X	X	X	X	X	X
SAFETY													
Adverse event	X ^d	X	X	X	X	X	X	X	X	X	X	X	X
REMINDERS													
HbA1c	X ^e												
Urine pregnancy test	X ^f												
Schedule nutritionist appointment	X												
Refer to exercise physiologist	X												

^a Demography consists of date of birth, sex, ethnicity, and race.

Novo Nordisk

Protocol No. NN8022-4432
UTN: U1111-1218-8104

^b Disallowed medications include GLP-1 RAs or SGLT-2 inhibitors for diabetes and any medication on- or off-label prescribed for weight loss other than the medication prescribed by the study clinician for chronic weight management (section 5.2.2.3). Use of these medications will be assessed during routine medication review at SMAs and entered into the eCRF.

^c If a subject does not attend the SMA at visit 13, a stepwise approach to obtaining weight data will be applied to obtain a month 12 weight measurement (-14 days, +28 days from scheduled month 12/visit 13): calling subject in for a month 12/visit 13 weight measurement, extract recent weight data from the electronic medical record, or use recent subject-reported weight.

^d Screening and randomization are one visit. Serious adverse event and pregnancy collection will begin after informed consent and randomization.

^e A POC HbA1c measurement will be performed at screening if an HbA1c measurement is not available within 90 days prior to randomization.

^f A urine pregnancy test will be performed prior to randomization in women of child bearing potential who are not using adequate contraception at the discretion of the study physician.

WPAI:SHP: Work Productivity and Activity Impairment Questionnaire Specific Health Problem; WLQ-8: Work Limitations Questionnaire Self-administered Short-Form; SMA: Shared Medical Appointment

Novo Nordisk

Protocol No. NN8022-4432
UTN: U1111-1218-8104

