3. Female who is pregnant, breast-feeding or intends to become pregnant or is of child-bearing potential and not using adequate contraceptive methods (adequate contraceptive measures as required by local regulation or practice).
4. Participation in another clinical trial within 30 days before screening.
5. Treatment with any medication with the intention of weight loss within 90 days before screening.

6. Previous or current participation in Cleveland Clinic's Integrated Medical Weight Management Program.
7. History of (or plans during the study period for) bariatric surgery, or use of minimally-invasive weight loss devices (i.e., intragastric balloons, lap bands) not removed within 1 year prior to screening.
8. History of type 1 or type 2 diabetes mellitus.
9. HbA1c \geq 6.5% at screening or within 90 days prior to randomization.
10. Any condition, unwillingness or inability, not covered by any of the other exclusion criteria, which, in the study clinician's opinion, might jeopardize the subject's safety or compliance with the protocol.

Study Procedures:

- Potentially eligible subjects will be identified during the course of routine implementation of Cleveland Clinic's Employee Wellness Program, "Healthy Choice," or referred to the study via the study advertisement or another health care provider.
- Study clinicians will obtain informed written consent from subjects and if eligible, subjects will be randomized to either WMP + Rx or WMP.
- Study data will be collected on electronic Case Report Forms (eCRFs) via an electronic data capture (EDC) system.
- Assessments at the screening and randomization visit (visit 1/baseline (month 0)) include: eligibility (including urine pregnancy test (if applicable) and point of care (POC) hemoglobin A1c (HbA1c) measurement if an HbA1c measurement is not available within 90 days prior to randomization), demographic data, relevant medical history, concomitant medications, height, and body weight.
- All subjects will enroll in the Integrated Medical WMP at the Cleveland Clinic's Endocrinology and Metabolism Institute. In this program, as part of usual care, subjects will:
 - discuss and choose one of three diet options: protein-sparing modified fast, Mediterranean, or meal replacement.
 - be referred to a nutritionist appointment.
 - initiate a series of twelve monthly study visits (visits 2-13) in the context of SMAs covering nutrition, physical activity, appetite control, sleep issues, and anxiety/depression/stress.

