 - be referred to an exercise physiologist for a personalized physical activity program.
 - if assessed relevant by the study clinician, be referred to a mental health specialist and/or sleep clinic.
- Subjects enrolled in the WMP + Rx arm will be provided a prescription for medication indicated for chronic weight management (obesity medication) at the time of randomization (visit 1).
- Disallowed medications:

- Other than the medication prescribed by the study clinician for chronic weight management in the WMP + Rx arm, use of any medication, on- or off-label, for weight loss purposes is not allowed in either arm during the study.
- The use of glucagon-like peptide-1 receptor agonists (GLP-1 RAs) and sodium-glucose co-transporter 2 (SGLT-2) inhibitors for diabetes diagnosed during the study is not allowed.
- Assessments during monthly study (i.e., SMA) visits include: weight, pregnancy and serious adverse events (SAEs), attendance at SMAs, and use of disallowed medications.
- Prescription fill data for obesity medication (WMP + Rx arm) will be collected from randomization through EOS.
- **Questionnaires:** PROs on work productivity and work limitations will be assessed by the Work Productivity and Activity Impairment Questionnaire Specific Health Problem v2.0 (WPAI:SHP) and the Work Limitations Questionnaire 8-Item (WLQ-8) Self-administered Short Form at visit 1, visit 7, and visit 13.

Study Duration: Total study duration for the individual subjects will be approximately one year. Subjects will be followed and data collection will continue for the full duration of the study, unless the subject withdraws informed consent. The full duration of the study is defined as up to and including visit 13. Effort will be made to obtain a month 12 (visit 13) weight measurement from all randomized subjects.

Analysis: Two estimands, each targeting a unique research question, have been defined to adequately describe the effect of an employer-based WMP combined with obesity medication compared to an employer-based WMP alone.

The primary estimand for all endpoints is an “intention-to-treat” estimand. This estimand will quantify the average treatment effect of an employer-based WMP combined with medication for chronic weight management compared to the employer-based WMP alone after 12 months, in all randomized subjects and regardless of adherence to randomized treatment.

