4.2.4 Subject Exclusion Criteria

Subjects presenting with any of the following exclusion criteria will not be eligible for the study:

1. Contraindications to all of the medications approved by the FDA for chronic weight management according to the label.
2. Previous participation in this study. Participation is defined as signed informed consent.
3. Female who is pregnant, breast-feeding or intends to become pregnant or is of child-bearing potential and not using adequate contraceptive methods (adequate contraceptive measures as required by local regulation or practice).
4. Participation in another clinical trial within 30 days before screening.
5. Treatment with any medication with the intention of weight loss within 90 days before screening.
6. Previous or current participation in Cleveland Clinic's Integrated Medical Weight Management Program.
7. History of (or plans during the study period for) bariatric surgery, or use of minimally-invasive weight loss devices (i.e., intragastric balloons, lap bands) not removed within 1 year prior to screening.
8. History of type 1 or type 2 diabetes mellitus.
9. HbA1c $\geq 6.5\%$ at screening or within 90 days prior to randomization.

- 10. Any condition, unwillingness or inability, not covered by any of the other exclusion criteria, which, in the study clinician’s opinion, might jeopardize the subject’s safety or compliance with the protocol.

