5.2.1 Subject Characteristics

Baseline assessments at the screening and randomization visit will include: eligibility (including urine pregnancy test (if applicable) and point of care (POC) hemoglobin A1c (HbA1c) measurement if an HbA1c measurement is not available within 90 days prior to randomization), demographic data, relevant medical history, concomitant medications, height, and body weight (as measured on a designated calibrated scale). Height and body weight will be recorded to one decimal place.

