5.2.2.2 Obesity medication (WMP + Rx arm only)

After randomization, subjects randomized to the WMP + Rx arm will initiate treatment with prescription medication indicated for chronic weight management (obesity medication). The prescription will be provided at the time of randomization (visit 1) as agreed between the study clinician and the subject, and this and any monitoring, counseling or follow-up will be consistent with usual clinical practice and standard of care. Medication choice, dose, and dose escalation will be at the discretion of the study clinician among those medications indicated for chronic weight management (Table 5-1). Only medications approved by the FDA for chronic weight management are allowed; all other medications for the purpose of weight management, on- or off-label, are not allowed.

Subjects in the WMP + Rx arm may switch to another obesity medication (switch), temporarily discontinue (suspend), or permanently discontinue (discontinue) obesity medication throughout the study according to standard clinical practice at the discretion of the study clinician. If a subject chooses to suspend or discontinue his/her obesity medication, he/she will be asked to notify the study clinician of his/her decision to ensure a safe withdrawal. In case of an obesity medication discontinuation, subjects will be encouraged to initiate treatment with another obesity medication (i.e., to switch) at the discretion of the study clinician according to routine practice.

Subjects who discontinue obesity medication will be encouraged to continue attending the study visits and assessments in their originally allocated treatment arm.

In order for the study to remain as close as possible to real-world conditions, subjects randomized to WMP + Rx arm will pay a nominal fee for the prescribed obesity medication simulating the co-payment patients would pay at a retail pharmacy if the medication was covered by their employer. The fee will be the same for all obesity medications utilized in the study regardless of market price. All prescription medications approved in the US for chronic weight management will be available for study subjects randomized to WMP + Rx (Table 5-1).

Table 5-1. Approved medications for chronic weight management in the US available in the study.

API (route of administration)	Brand name	Year of FDA approval
Orlistat (p.o.)	Xenical®	1999
Lorcaserin/Lorcaserin extended-release (p.o.)	Belviq®/Belviq XR®	2012

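### The only stated rule for the pre-randomization pregnancy test names women already excluded by criterion 3, so no woman who could be randomized is directed to be tested

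*Protocol*

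**What the plan says.** Four parts of the protocol bear on this point.

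- **Who is tested.** Appendix 1-1, footnote f, places a urine pregnancy test before randomization "in women of child bearing potential who are not using adequate contraception at the discretion of the study physician". The schedule marks the test at visit 1 only.
- **Who is excluded.** Section 4.2.4, criterion 3, excludes a "Female who is pregnant, breast-feeding or intends to become pregnant or is of child-bearing potential and not using adequate contraceptive methods". The synopsis repeats the criterion.
- **What the test is for.** Section 5.2.1 and the synopsis place the test under eligibility, in the form "eligibility (including urine pregnancy test (if applicable". Neither says when it is applicable.
- **What happens around it.** Section 5.2.2.2 states for the WMP + Rx arm: "The prescription will be provided at the time of randomization (visit 1) as agreed between the study clinician and the subject". Footnote d of Appendix 1-1 states that screening and randomization are a single visit and adds: "Serious adverse event and pregnancy collection will begin after informed consent and randomization". Section 7.3.1 agrees: "Pregnancies will be reported from the time a subject is randomized until EOS at month 12". After visit 1, pregnancy is next assessed at the monthly visits (synopsis, Study Procedures: "Assessments during monthly study (i.e., SMA) visits include: weight, pregnancy and serious adverse events (SAEs").

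The SAP has no instruction on pregnancy testing.

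**The concern.** A test used to determine eligibility should be done in people whose eligibility is still open. Footnote e, on HbA1c, works that way: the point-of-care test is done when no recent value exists. Footnote f does the reverse. It names women whose ineligibility is already settled by their contraceptive status, and passes over those for whom a positive result would change the decision.

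What is at stake is subject safety and the enforcement of criterion 3, not the inference. Criterion 3 excludes pregnancy, but no directed test checks that part of it in any woman who can be randomized. Because the drug is prescribed at the same visit, every later pregnancy check comes after the first prescription. An early pregnancy that a woman using contraception does not know about would be found before prescribing only if the clinician chose to test her.

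**Working it through.** The plan gives no figure to reproduce. The check is a comparison of two groups, followed by simple arithmetic on how many women are affected.

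**Step 1: compare the groups.**

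- T, the women footnote f directs to be tested: of child-bearing potential AND not using adequate contraception.
- E, the women criterion 3 excludes: pregnant OR breast-feeding OR intending pregnancy OR (of child-bearing potential AND not using adequate contraception).

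T is the fourth limb of E. Every member of T is therefore in E, and no woman is both in T and eligible. By the protocol's own definitions, 0% of eligible women of child-bearing potential are directed to be tested.

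**Step 2: look for another rule.** Section 5.2.1 and the synopsis mention the test without naming a group. The schedule row leads only to footnote f. No other testing rule appears in either document.

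**Step 3: allow for the discretion clause.** It can attach to the test or to the judgement of whether contraception is adequate. On the first reading the test is optional even within T. On the second the physician decides who belongs to T. On neither does the rule reach women judged to be using adequate contraception.

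**Step 4: time to the next scheduled check.** Visit 2 is at month 1 with a window of ±14 days (Appendix 1-1). With a 30-day month, 30 − 14 = 16 and 30 + 14 = 44, so the next check falls between day 16 and day 44.

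**Step 5: number of women affected.** Planned randomization is 200 at 1:1 (Protocol 4.2.5 and 4.2.6), so 200 ÷ 2 = 100 subjects are in the WMP + Rx arm. The documents do not give the share who are women of child-bearing potential; 20% to 60% is assumed.

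| Assumed share | WMP + Rx women prescribed with no directed test | Tests among 240 screened if all such women are tested |
|---|---|---|
| 20% | 0.20 × 100 = 20 | 0.20 × 240 = 48 |
| 60% | 0.60 × 100 = 60 | 0.60 × 240 = 144 |

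The middle column counts women without a directed test. It does not count women who would in fact go untested, or pregnancies. Neither can be estimated from the documents.

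**The case against.** The strongest reply is that this is a pragmatic trial that deliberately leaves such checks to routine care. Section 5.2.2.2 says that prescribing and any monitoring follow usual practice and the standard of care. The test sits under the reminders heading of the schedule, and the qualifier in section 5.2.1 is open enough to cover any woman. Clinicians may well test before prescribing, and nothing prevents it. The test is also not the only check: criterion 3 is assessed in every woman at visit 1, medical history is taken, and criterion 10 lets the clinician exclude on safety grounds. What remains uncovered is an unrecognized early pregnancy in a woman using contraception, and no rate for that can be given. All of this stands, and it limits the size of the problem.

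It does not rescue the rule. Permission to test more widely is not a direction to do so, and a site that follows the schedule literally will test women who cannot enter and need not test those who can.

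A second reply is that a woman might start an adequate method, or have one whose adequacy is in doubt, so that a test could decide her entry. No text describes that route. Screening and randomization are one visit, and criterion 2 treats signed consent as previous participation, so she could not come back later. Even if she qualified on the day, established contraception users would still have no directed test.

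A third reply is that mandatory testing adds a protocol-driven procedure where a lighter clarification, such as testing women of child-bearing potential according to usual practice, would remove the redundancy. That wording would correct the group, but it would again leave testing before the first prescription to choice.

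**Conclusion.** The point holds. The one stated testing rule is aimed at the wrong group: it coincides with a limb of exclusion criterion 3 and so cannot serve the eligibility purpose that section 5.2.1 assigns to the test. The protocol's passages can all be followed literally without contradiction; the fault is in whom the rule names.

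That the rule reaches no eligible woman follows from the text and needs no assumption. The figure of 20 to 60 women in the WMP + Rx arm rests entirely on the assumed 20% to 60% share, and the day 16 to day 44 gap on a 30-day month. Endpoints, estimands, power, alpha and sample size are unaffected. The rule should be corrected because it governs a safety check made just before a drug is prescribed.

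**What to change.** Reword footnote f along these lines: *Before randomization, every woman of child-bearing potential has a urine pregnancy test; a positive result makes her ineligible under exclusion criterion 3.* In the synopsis and section 5.2.1, define the test as applicable to women of child-bearing potential, so that all three places state the same rule.

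The change is one sentence and one definition. It needs no new visit, since the test is already scheduled at visit 1. The cost is some additional urine tests at that visit, at most about 48 to 144 among the 240 planned screened subjects under the same assumed share, and fewer where clinicians would have tested anyway.
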